##### **10.5.4.2 Headache recurrence**

The proportion of subjects with headache recurrence (moderate or severe headache at baseline, which became pain free at 2 hours post-dose and worsened again up to 48 hours post-dose) will be evaluated based on first dose. The frequency of recurrence will be compared by the same logistic regression model used for the primary endpoint analysis. The significance level of this exploratory analysis will be a nominal one-sided 0.05.

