## **10.7 Missing Values**

The primary and key secondary endpoints are defined as proportions. If a subject has a missing value for a proportion endpoint, the subject will be classified as a nonresponder for this endpoint. Subjects who have more than one symptom (nausea, phonophobia or photophobia) but do not select one as the MBS prior to dosing, will be considered inevaluable for the MBS endpoint as there is no MBS selected to evaluate. In the case of subjects that have only one symptom (nausea, phonophobia, or photophobia) at predose but do not select a MBS, the one symptom will be considered the MBS for analysis.

For subjects who do not record a symptom rating, that symptom (pain, photophobia, phonophobia or nausea) will be assumed to be present at all time points where data are missing. Subjects who do not provide a headache severity rating at baseline will be assumed to have all four symptoms (pain, nausea, photophobia and phonophobia) at all time points. If recurrence medication is taken within 24 hours post dosing, or from 24 hours to 48 hours post dosing, even if no headache is reported, headache recurrence will be assumed for the first dose analysis.

The sensitivity analysis for handling missing data is described in detail in the SAP.

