 - The time intervals are 30 minutes, 1 hour, 1.5 hours, 2 hours, 3 hours, 4 hours, 24 hours, and 48 hours after the first dose of study medication. The e-diary sets the post dose assessments based on the recorded time of dosing. A subject that begins reporting their migraine at the exact time of dosing will have all of the post dose assessment time points available to them. If a subject starts recording their information in the e-diary after they dose including the time of dosing, the assessments that become available for them are based on the time of dosing, relative to when they accessed the e-diary. For example, if at 1-hour post actual dosing the subject initiates migraine mode and begins entering data into the e-diary, the subject will be allowed to respond to the initial questions about their migraine and time of dosing and then based on the time they record for dosing they automatically will miss subsequent time points, i.e.; the 30 minute and 1-hour time points. A missed time point is missed.
 - Alarms occur at the predefined time points to remind the subject it is time to complete the assessments. The Migraine Questions button is always available, but the subject is not be able to answer the questions until prompted by an alarm within a study migraine.
- Migraine Mode – Second Dose (Optional)
 - The subject should only take a second dose of study medication if the migraine pain is not gone by two hours after the first dose or the migraine pain was gone and came back two hours or more after the first dose (up to 24 hours after first dose).
 - The Dose 2 button will appear AFTER the e-diary recognizes 2 hours have passed since the first dose and remains until the 24-hour time point.
 - During the 2-hour post dose assessment the subject will be asked to indicate if he/she would like to take a second dose of study medication
 - If a second dose is reported alarm intervals are the same as for the reporting of the first dose and any remaining alarms from the first dose are cancelled. However, if

the subject inadvertently enters a dosing time of the second dose occurring prior to the first dose the first dose alarms do not stop and subject can therefore response to post-dose assessments based on time of dosing of first dose, therefore not really assessing their response to the second dose.

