5.2 Analysis of First and Second Doses

Any analyses based on first dose will only include data observed up to the time of dosing with a second dose. These summaries will be presented based on the first dose taken. The exception to this is the primary and secondary endpoints at the 2-hour time point; if a second dose is taken before the 2-hour time point, the subject will still be included in the summary at 2 hours and will be analysed as having not achieved headache pain-free or MBS-free status at 2 hours.

Any analyses based on the second dose will only include data observed on or after the time of dosing with a second dose. These summaries will be presented by treatment sequence, listed in Section 2.3. Analyses based on the second dose will be done for both the rescue and recurrence subpopulations.

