11.7.10 Incidence of Rescue or Recurrence Medication Use

The count and percentages of subjects who take rescue or recurrence medication will be presented by treatment group and time point. The summary will be based on first dose using the ITT population.

The summary of study rescue or recurrence medication use will use the following three time points as applicable:

- At 2-hours post first dose
- Greater than 2, but less than or equal to 24 hours post first dose
- Greater than 24, but less than or equal to 48 hours post first dose

The combined summary of all rescue or recurrence medication use will use the following three time points as applicable:

- Less than or equal to 2 hours post first dose
- Less than or equal to 24 hours post first dose
- Less than or equal to 48 hours post first dose

A subject is defined to have used rescue medication within the specified time point if the subject takes a second dose of study drug within the time point or answers “Yes” to the e-diary question asking if any other medications have been used since the start of the migraine, and the medication is not considered a recurrence medication.

A subject is defined to have used recurrence medication if he or she records a mild (1), moderate (2), or severe (3) headache at baseline which becomes pain-free at 2 hours after the first dose, becomes more severe up to 48 hours after the first dose, and the subject takes a second dose of study drug within the time point or answers “Yes” to the e-diary question asking if any other medications have been used since the start of the migraine.

If the subject becomes pain-free at 2 hours after the first dose and records the use of rescue medication, but no headache severity is recorded between 2 hours after the first dose and the time of administration of a second dose, it will be assumed that the medication is taken for recurrence.

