11.7.11 Incidence of Headache Recurrence

The counts and percentages of subjects who experience headache recurrence will be presented by treatment group. The summary will be based on first dose using the ITT population.

A subject is defined to have experienced headache recurrence if they record a mild (1), moderate (2), or severe (3) headache at baseline which becomes pain-free at 2 hours post first dose and then becomes more severe up to 48 hours post first dose.

If the subject becomes pain-free at 2 hours post first dose and records the use of rescue medication, but no headache severity is recorded, it will be assumed that the medication is taken for recurrence, and the subject will be counted as having experienced headache recurrence.

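### SAP 11.7.10 and 11.7.11 narrow the protocol's recurrence rule without declaring it: 2-hour responders who medicate a returned headache but have only 0 ratings are counted as having no recurrence

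*SAP*

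**What the plan says.** **Protocol.** Section 10.5.4.2 defines recurrence as a headache, moderate or severe at baseline, that "became pain free at 2 hours post-dose and worsened again up to 48 hours post-dose". Section 10.7 adds a rule for subjects who medicate. It covers recurrence medication in the first 24 hours and in the following 24 hours: "even if no headache is reported, headache recurrence will be assumed for the first dose analysis".

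**SAP.** Section 11.7.11 gives two routes to recurrence.

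- Route 1 is recorded worsening: a headache at baseline "which becomes pain-free at 2 hours post first dose and then becomes more severe up to 48 hours post first dose", whether or not anything was taken.
- Route 2 is medication: if a 2-hour pain-free subject "records the use of rescue medication, but no headache severity is recorded, it will be assumed that the medication is taken for recurrence".

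Section 11.7.10 makes a similar assumption for recurrence-medication use, on the condition that "no headache severity is recorded between 2 hours after the first dose and the time of administration of a second dose". Medication that does not qualify as recurrence medication is classed there as rescue.

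Two other SAP sections determine which ratings can exist and be used. In Section 5 the first-dose prompts after 2 hours fall at 3, 4, 24 and 48 hours. The question button stays visible, "but the subject is not be able to answer the questions until prompted by an alarm within a study migraine". Section 5.2 adds: "Any analyses based on first dose will only include data observed up to the time of dosing with a second dose".

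Section 5.1 lists changes from the planned analysis, including the admission of headaches that were mild at dosing. It does not mention the recurrence rule.

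**The concern.** Under the protocol, recurrence medication is enough to establish recurrence. Under the SAP it is enough only when the severity is missing. None (0) is one of the severity levels in SAP 8.5, and SAP 5.3 describes missing data as a failure to record a severity. A 0 is therefore a record, not a gap.

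Take a subject who is pain-free at 2 hours and rates 0 at 3 and 4 hours. The headache returns at 10 hours, the subject takes an analgesic, and the 24- and 48-hour ratings are again 0. No rating was prompted while the pain was present. Route 1 fails because no rating worsened, and Route 2 fails because ratings exist. The subject has no recurrence, and the medication becomes rescue by default.

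That leaves the SAP at odds with itself. SAP 4.1 and Protocol 10.6.1 reserve second-dose rescue for subjects who were not pain-free at 2 hours. SAP 11.7.2 would count the example subject as failing sustained pain freedom because of the medication, while the recurrence table shows no recurrence. At stake are the exploratory first-dose tables of recurrence and of rescue or recurrence medication use.

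**Working it through.** **1. The rules side by side, for a subject pain-free at 2 hours**

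- A usable later rating above 0, with medication: recurrence under the protocol, and under the SAP by Route 1.
- Medication, no later severity on file: recurrence under both.
- Medication, all usable later first-dose ratings 0: recurrence under Protocol 10.7 if the medication is recurrence medication; no recurrence under SAP 11.7.11.
- Second dose taken, pain rated only at second-dose Hour 0: recurrence under the protocol; unsettled under the SAP. Section 5.2 keeps first-dose data up to the second dose and assigns data on or after it to the second-dose analysis.

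The gap is the third line, and the fourth if the Hour-0 rating is excluded.

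**2. The windows.** Section 11.7.11 gives no window for the missing severity. A 2-hour responder has a 2-hour rating by definition, so the clause works only if it means ratings after 2 hours. Section 11.7.10 starts its window at 2 hours but ends it at the second dose, so the window has no end for someone who took only other medication. Two programmers could produce different tables.

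**3. The design figure.** The documents give no recurrence rate. The sample-size sections (Protocol 10.1, SAP 2.2) give 2-hour pain-free rates of 7.4% (placebo), 13.9% (50 mg), 13.6% (100 mg) and 18.8% (200 mg), with 570 per arm and one-sided alpha 0.025. They state power above 90%.

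Power = Φ{[(p1 − p0) − 1.96·√(2p̄(1−p̄)/n)] / √[(p0(1−p0) + p1(1−p1))/n]}, with p̄ the mean of p0 and p1, gives 94.6%, 92.8% and above 99.9% for 50, 100 and 200 mg. The stated figure reproduces.

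**4. Subjects who can be affected.** Only 2-hour responders can be missed. Per 570:

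- placebo: 570 × 0.074 = 42.2
- 50 mg: 570 × 0.139 = 79.2, ratio to placebo 1.88
- 100 mg: 570 × 0.136 = 77.5, ratio 1.84
- 200 mg: 570 × 0.188 = 107.2, ratio 2.54

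**5. Absolute loss.** Missed = responders × r × f. Here r is the share of responders who medicate a returned headache, and f is the share of those whose usable later ratings are all 0. Neither is in the documents. For illustration, assume r = 10–40% and f = 10–50%, equal in all arms:

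- placebo: 42.2 × 0.01 to 42.2 × 0.20 = 0.4 to 8.4 subjects (0.07–1.5% of the arm)
- 50 mg: 0.8 to 15.8 (0.14–2.8%)
- 100 mg: 0.8 to 15.5 (0.14–2.7%)
- 200 mg: 1.1 to 21.4 (0.19–3.8%)

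**6. Proportional loss.** If ρ is the true recurrence rate among responders, the fraction missed is (responders × r × f) / (responders × ρ) = r·f/ρ. The number of responders cancels. With r, f and ρ equal across arms, every arm's recurrence count is understated by the same proportion.

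**The case against.** The strongest objection is that the wording may be meant as the protocol means it. The SAP's clause about no recorded severity could be shorthand for no headache having been reported. Read literally, answering any prompt between 2 hours and the medication would defeat Route 2, leaving it almost empty. This is plausible, but a programmer will code what is written, and a 0 is a recorded severity. If the protocol's meaning was intended, the amendment only confirms it.

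Other points stand and limit the concern:

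- A reader might infer that a medicated responder counts only if no rating exists. That is wrong, because Route 1 counts any usable later worsening.
- A reader might infer that medication is the only trace of the returned pain. Protocol 9.1.8.2 has the subject note when the headache returned and grade the pain at the second dose. Neither SAP section on recurrence names these as inputs, but the protocol plans their collection. A high share of all-0 cases therefore cannot be presumed.
- Whether second-dose takers are lost depends on how Section 5.2 is read. It does not clearly exclude the Hour-0 rating.
- Protocol 7.3.2 describes recurrence treatment only as a second dose of study drug, allowed up to 24 hours. The 24–48 hour part of Protocol 10.7 points to other medication without saying so. Extending the rule to non-study medication rests on that and on the definition in SAP 11.7.10.
- The combined medication summary in 11.7.10 pools rescue and recurrence use, so misclassification between them cannot change it.

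**Conclusion.** The SAP's medication rule is narrower than Protocol 10.7, and SAP 5.1 does not say so. As written, a 2-hour responder who medicates a returned headache and has only 0 ratings in the usable first-dose data is counted as having no recurrence. The medication is classed as rescue, which for second-dose takers conflicts with SAP 4.1 and Protocol 10.6.1.

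The number affected cannot be derived from the documents; the ranges above illustrate assumed inputs. If conditional rates are equal across arms, the absolute loss in a lasmiditan arm is about 1.8 to 2.5 times the placebo loss. A reader might go further and infer that the rule distorts the comparison in favour of lasmiditan. The documents do not support that. The larger count comes from having more responders, the proportional understatement is then the same, and no document gives re-medication or rating patterns by arm. Equal absolute losses would need a placebo conditional loss rate 1.84 to 2.54 times that of the lasmiditan arm.

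The tables concerned are exploratory. The primary and key secondary tests and their type I error control are untouched.

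**What to change.** Replace the last paragraph of SAP 11.7.11 and the matching paragraph of 11.7.10 with one rule based on Protocol 10.7. A subject pain-free at 2 hours counts as having recurrence and as having used recurrence medication if, after 2 hours and up to 48 hours after the first dose, the subject takes a second dose or reports other medication meeting the 11.7.10 definition. Ratings of 0 do not override this. State also that the second-dose Hour-0 severity and the diary time of headache return count as evidence of recurrence in the first-dose analysis, notwithstanding Section 5.2.

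If the narrower rule is intended, declare and justify it in SAP 5.1, give it one window in both sections, and say how 0 ratings are treated.

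The cost is SAP wording and one derivation, using data the protocol already plans to collect. The reported lasmiditan recurrence rate may be slightly higher. Some medication taken for other reasons may be counted, because the diary question cited in 11.7.10 asks about any other medication since the migraine began and does not establish why it was taken.

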11.7.12 Patient Global Impression of Change

Counts and percentages of the level of patient global impression of change (PGIC) will be presented by treatment group at the 2-hour post-dose time point. This will be summarized based on the first

dose using the ITT population, and based on the second dose for recurrence and rescue using the ITT-2nd Dose population.

Patient global impression is measured on a seven-point scale.

- Very much better
- Much better
- A little better
- No change
- A little worse
- Much worse
- Very much worse

Treatment comparisons between the lasmiditan groups and placebo will be tested using the Cochran-Mantel-Haenszel test statistic using modified ridit scores, controlling for background use of medication to reduce the frequency of migraine episodes.

A bar graph of the proportion of subjects with responses of “Much better” or “Very much better” to subjects with any other, or a missing, response at the 2-hour post-dose time point will be presented based on first dose using the ITT population, and based on the second dose for recurrence and rescue using the ITT-2nd Dose population.

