## 5.3 Additional Objectives

To explore the effect and time course of a second dose of lasmiditan 50 mg, of lasmiditan 100 mg and of lasmiditan 200 mg compared to placebo on relief of pain and MBS when used for rescue and for recurrence of migraine. To explore resource utilization during the study compared to pre-study in terms of cardiovascular events and in terms of migraine episodes.

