2.3 Randomization

Subjects will be centrally randomized to one of 7 treatment sequences to receive lasmiditan 50 mg (L50 mg), lasmiditan 100 mg (L100 mg) or lasmiditan 200 mg (L200 mg) or placebo (P) for the first dose (in a 1:1:1:1 ratio) and a second dose for rescue or recurrence of migraine (if needed). Subjects will be stratified (yes or no) for current use of concomitant medication(s) that reduce the frequency of migraine episodes. Study drug will be randomized and dispensed at Visit 1 as follows:

First dose for treatment of migraine	Second dose for rescue or recurrence of migraine (if needed)
L50 mg	L50 mg
	L50 mg
	placebo
L100 mg	L100 mg
	L100 mg
	placebo
L200 mg	L200 mg

	L200 mg
	placebo
Placebo	placebo

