11.7.9 Disability

Counts and percentages of the level of disability will be presented at the 0.5, 1, 1.5, 2, 3, 4, 24, and 48-hour post-dose time points. This will be summarized based on the first dose using the ITT population, and based on the second dose for recurrence and rescue using the ITT-2nd Dose population.

Disability is measured on a four-point scale.

- Not at all (0)
- Mild interference (1)
- Marked interference (2)
- Completely, needs best rest (3)

Treatment comparisons between the lasmiditan groups and placebo will be tested using the

Cochran-Mantel-Haenszel test statistic using modified ridit scores, controlling for background use of medication to reduce the frequency of migraine episodes.

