11.7.18 Time to MBS-Free After Second Dose

The time to MBS-free after second dose will be presented by treatment group using a Kaplan-Meier analysis. This summary will be presented for the ITT-2nd Dose population, and separately for subjects taking a second dose for rescue or recurrence.

The number of subjects experiencing MBS-free, and the number of subjects censored, will be summarized. The Kaplan-Meier estimates, and 95% confidence intervals calculated using the log-log transformation, of the number of hours for 25%, 50%, and 75% of subjects to experience MBS-free will be presented. The Kaplan-Meier estimate, and 95% confidence interval, of the probability of experiencing MBS-free will be presented at the 0.5, 1, 2, 4, and 24-hour post-dose time points.

Time to MBS-free will be calculated as:

date/time a lack of presence of the MBS chosen at the time of second dosing is reported –
date/time of second dosing

Subjects who do not record the disappearance of their second-dose MBS, or who record such a response after 24 hours post second dose will be censored at the time of their last non-missing post second dose symptom assessment at or before 24 hours. Subjects with missing MBS at the time of second dose will be censored at the time of second dose. Subjects who report that no symptoms were present at the time of second dose will be excluded from the analysis.

A figure of the Kaplan-Meier analysis will also be presented.

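### The SAP never specifies the randomised second-dose contrast (active v placebo second dose within the same lasmiditan arm), and the PGIC test as written mixes first-dose effects into the second-dose comparison

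*SAP*

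**What the plan says.** **Objective and design.** Protocol 5.3 sets an exploratory objective for the second dose: each of the three lasmiditan strengths is to be judged "compared to placebo on relief of pain and MBS when used for rescue and for recurrence of migraine". In SAP 2.3, "Subjects will be centrally randomized to one of 7 treatment sequences". The sequence table lists two active rows and one placebo row for the second dose in each lasmiditan arm, and placebo only in the placebo arm. The 2:1 ratio is inferred from those rows; it is not written out.

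**General rule.** For second-dose analyses SAP 5.2 states: "These summaries will be presented by treatment sequence, listed in Section 2.3". Sections 11.7.13 to 11.7.17 (pain-free, relief, the times to each, and MBS-free after the second dose) follow it, separately for rescue and recurrence.

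**Departures from the rule.**
- 11.7.12 (PGIC) is presented by treatment group and covers both doses. Its one test sentence reads "Treatment comparisons between the lasmiditan groups and placebo will be tested using the" Cochran-Mantel-Haenszel statistic, controlling only for background preventive use.
- 11.7.9 (Disability) is also summarised "based on the second dose for recurrence and rescue using the ITT-2nd Dose population", with the same test sentence and no stated grouping.
- 11.7.18: "The time to MBS-free after second dose will be presented by treatment group using a Kaplan-Meier analysis". No test is named.
- 11.7.19 (meaningful relief) also reports second-dose results by treatment group.

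SAP 2.1 and 2.2 define the treatment group by the first dose. The default model in SAP 11 has treatment group as its covariate, although the Firth provision there refers to groups formed by treatment sequence and subpopulation. No section says which sequences are contrasted.

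**The concern.** Whether a subject takes the second dose depends on the response to the first and on the subject's own choice, and both precede a blinded second dose. Within one lasmiditan arm, users of L/L and L/P are therefore comparable by randomisation, apart from those lost for lack of an assessment after the second dose. Users of P/P are not comparable with either. They reached the second dose by failing, or relapsing after, placebo, and they carry no first-dose drug.

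A test of first-dose group against placebo on second-dose data therefore does not isolate the second dose. It could show an effect when the second dose does nothing, or dilute or hide a real one. The L/P subjects, who are the valid comparator, would sit on the active side of the comparison.

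**Working it through.** **1. The plan's nearest figure.** Neither document gives a sample size or power for a second-dose comparison. The first-dose claim of more than 90% power with 570 per arm (SAP 2.2) can be checked with

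power = Φ[(p2 − p1 − z·SE0)/SE1], where SE0 = √(p̄(1−p̄)(1/n1+1/n2)) and SE1 = √(p1(1−p1)/n1 + p2(1−p2)/n2).

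For 100 mg (7.4% v 13.6%, one-sided 0.025): SE0 = 0.01816, SE1 = 0.01807, and (0.062 − 1.96×0.01816)/0.01807 = 1.46, so power is 92.8%. The 50 mg dose gives 94.6% and the 200 mg dose more than 99.9%. The claim reproduces.

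**2. What each second-dose contrast estimates.** Let response after the second dose be m in P/P, m + d1 in L/P and m + d1 + d2 in L/L. Here d1 is first-dose carry-over plus selection, and d2 is the second-dose effect.
- L/L − L/P = d2
- L/L − P/P = d1 + d2
- first-dose group − P/P = (2/3)(d1 + d2) + (1/3)d1 = d1 + (2/3)d2

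Only the first isolates d2. With d2 = 10 points and d1 = 0, the pooled contrast shows 6.7 points.

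**3. Selection at the plan's own rates (7.4% placebo, 18.8% at 200 mg).** Not pain-free at 2 hours, hence eligible for rescue: 92.6% v 81.2%. Pain-free, hence open to recurrence: 570×0.074 = 42 v 570×0.188 = 107 subjects. These describe eligibility, not use.

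**4. Direction.** Suppose everyone who responds to placebo would also respond to 200 mg. Then 11.4/92.6 = 12.3% of placebo rescue candidates are subjects 200 mg would have cleared, and the 200 mg rescue group has none. If such subjects later clear at 40% and others at 10% (assumed), P/P shows 0.123×0.40 + 0.877×0.10 = 13.7% against 10.0%. Selection alone then works against lasmiditan by 3.7 points, or 1.8 points at 30% and 15%. Carry-over of first-dose drug would usually work the other way, so the sign of d1 is open.

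**5. Size of the error.** Assume d2 = 0, 20% response in P/P, and 30% to 50% of 570 per arm taking a second dose, equal across arms. P/P and the first-dose group are then 171 to 285 each, and L/L is 114 to 190. A binary response stands in for the ordinal scale. Chance of p<0.05, two-sided (the level SAP 11 sets for exploratory tests):

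| d1 | First-dose group v P/P | L/L v P/P | L/L v L/P |
|---|---|---|---|
| −5 points | 23%–35% | 18%–28% | 5% |
| 0 | 5% | 5% | 5% |
| +5 points | 20%–30% | 17%–26% | 5% |
| +10 points | 57%–79% | 49%–70% | 5% |

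**6. The contrast the design provides.** 570 splits into 380 L/L and 190 L/P per lasmiditan arm, times uptake. Power is at two-sided 0.05, with rescue and recurrence combined and second-dose response rates assumed:

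| Uptake | Per arm, L/L v L/P | 18.8% v 7.4% | 13.6% v 7.4% | Three arms together | 18.8% v 7.4% | 13.6% v 7.4% |
|---|---|---|---|---|---|---|
| 20% | 76 v 38 | 34% | 14% | 228 v 114 | 83% | 38% |
| 30% | 114 v 57 | 50% | 20% | 342 v 171 | 95% | 55% |
| 60% | 228 v 114 | 83% | 38% | 684 v 342 | >99% | 86% |

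**The case against.** The strongest defence is that the endpoints named in the second-dose objective are pain and MBS, and 11.7.13 to 11.7.17 present nearly all of them by sequence, as Protocol 10.6.1 and 10.6.2 planned. L/L and L/P can be read side by side there. A reader might infer that the whole second-dose objective gets a confounded answer; the documents do not support that. PGIC and Disability are not named in the objective.

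Three narrower objections also stand.
- 11.7.18 is a Kaplan-Meier summary without a test. It is a wording conflict with 5.2, not a chosen pooled test.
- The test sentence in 11.7.9 serves both doses, and 5.2 would put its second-dose summary by sequence. Its comparator is undefined, not expressly P/P.
- The Firth provision in SAP 11 points to sequence-level models, so it is not established that L/P is never used as a comparator.

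What the defence does not supply is a named contrast. Even if 5.2 overrides the grouping in 11.7.12, its test sentence does not say which sequences are compared, and neither does SAP 11. The Protocol synopsis promises exploratory second-dose comparisons between treatment groups without defining them. Columns side by side do not replace a specified contrast when tests are planned, and leaving it open allows a choice after unblinding.

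**Conclusion.** The point holds as a gap in exploratory analyses. The SAP plans tests on second-dose data without specifying the randomised contrast. In 11.7.12, read as written, it specifies one that combines first-dose carry-over and selection with a diluted second-dose effect. Sections 11.7.18 and 11.7.19 conflict with 5.2 on presentation.

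The size of the bias cannot be fixed from the documents. Uptake, second-dose response rates and d1 are all assumed, and the 2:1 split is inferred. A reader might take the 3.7-point illustration as the expected bias against lasmiditan. It is not: it rests on assumed clearance rates and a monotone response, concerns a pain endpoint that is already presented by sequence, and leaves out carry-over. The net direction is unknown.

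SAP 5.1 calls the second-dose analyses exploratory, and they lie outside the gatekeeping sequence in 11.1. No primary or key secondary conclusion changes.

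**What to change.** Before unblinding:
- State in SAP 5.2 and 11 that any second-dose test compares L/L with L/P within the same first-dose arm, separately for rescue and recurrence.
- Add one estimate of the second-dose effect stratified by first-dose level and preventive-use stratum.
- Show P/P descriptively, or label any comparison with it as a whole-regimen comparison and not a second-dose effect.
- Separate the first-dose and second-dose test sentences in 11.7.9 and 11.7.12, and present second-dose results in 11.7.12, 11.7.18 and 11.7.19 by sequence.

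The cost is SAP wording and programming on the same data. The drawback is precision: per-dose groups are smaller than in a comparison with P/P (114 v 57 at 30% uptake, 228 v 114 at 60%), so intervals widen, and splitting rescue from recurrence shrinks them further. The stratified estimate recovers part of this.
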